List of Abbreviations

AE	Adverse Event
AQ	aminoquinoline
AQ-13	Investigational aminoquinoline active against CQ- and multi-resistant Plasmodium falciparum parasites (n -propyl side chain)
AQ-72	mono- N -dealkylated metabolite of AQ-13
AQ-73	di- N -dealkylated metabolite of AQ-13
AUC	Integrated area under the curve of drug blood levels over time, which is used as a measure of oral bioavailability
β-hCG	Beta Human Chorionic Gonadotropin
BP	Blood Pressure (mm Hg)
C	Comparator (Coartem in these studies)
CBC	Complete Blood Count
CDC	Centers for Disease Control (and Prevention)
CFA	West African Franc (\$1.00 US=500 CFA)
CFR	Code of Federal Regulations
CK	Creatine Kinase
CI	Clearance of drug from the blood (by excretion or conversion to metabolites inactive against CQ-resistant parasites)
CPD	Citrate Phosphate Dextrose (anticoagulant)
CQ	chloroquine
CRF	Case Report Form
CYP450	Cytochrome P-450
DMID	Division of Microbiology and Infectious Diseases, NIAID, NIH
DSMB	Data and Safety Monitoring Board
ECG	ElectroCardioGram
EDTA	Ethylene Diamine Tetra-acetic Acid (anticoagulant)
F	Constant to adjust pharmacokinetic data for oral dosing
FDA	Food and Drug Administration
FWA	Federal-Wide Assurance (number)
GCP	Good Clinical Practice
G6PD	Glucose-6-Phosphate Dehydrogenase
H_0	Null hypothesis
H_1	Alternative hypothesis
Hb	Hemoglobin
Hct	Hematocrit
HPLC	High Performance Liquid Chromatography
ICH	International Conference on Harmonisation
ID	Identification (study) number for study participants
ICMJE	International Committee of Medical Journal Editors
IEC	Independent or Institutional Ethics Committee

List of Abbreviations - *continued*

IND	Investigational New Drug (Application)
IRB	Institutional Review Board
ITT	Intent-to treat (analysis)
K76T	Lysine to Threonine point mutation at position (amino acid) 76
M	Margin of non-inferiority
MOP	Manual of Procedures
MRT	Mean Residence Time
N	Number (typically refers to subjects)
NIAID	National Institute of Allergy and Infectious Diseases, NIH, DHHS
NIH	National Institutes of Health
OHRP	Office for Human Research Protections
OOPD	Office of Orphan Product Development (FDA)
ORA	Office of Regulatory Affairs, DMID, NIAID, NIH, DHHS
P	Placebo
PCR	Polymerase Chain Reaction
PE	Physical Examination
pfCRT	Plasmodium falciparum Chloroquine Resistance Transporter
PI	Principal Investigator
QT	Interval from the beginning of ventricular depolarization (start of QRS) to the conclusion of repolarization (end of T wave)
QTc	QT interval adjusted (corrected) for heart rate
SAE	Serious Adverse Event
SOP	Standard Operating Procedure
t $\frac{1}{2}$	Half-Time (for concentration to decrease by 50%)
V_d	Volume of distribution (Liters)
WBC	White Blood Cell
WHO	World Health Organization
X	the percentage of the efficacy of the active control vs. placebo (C – P) that one desires to retain in the investigational drug (I) (see the Statistical Section on pages 37-40)

Title:	AQ-13 for Uncomplicated P. falciparum Malaria: Proof of Concept Study
Population:	Adult Malian males with uncomplicated Plasmodium falciparum Malaria This study will include adult Malian males ≥ 18 years of age in good general health (who have no known medical conditions other than malaria). Subjects who agree to participate and provide their informed consent will be randomized to one of two study arms (33 per arm \times 2 arms = 66 subjects) to receive either AQ-13 (1596 mg orally over 3 days) or Coartem (4 tabs twice daily \times 3 days).
Number of Sites:	There are several initial screening sites at: 1] the Missira/Sirakoroba Community Health Center in the Kolokani District and 2] referral outpatient clinics in and near Bamako. Although there is only one inpatient study site at the Clinical Research Center in Bamako, there will be two study follow-up sites for the 5 weeks of outpatient follow-up: the Community Health Center for Missira and Sirakoroba and the Clinical Research Center in Bamako.
Study Duration:	The duration of this study will be up to 15 months (including follow-up), beginning on June 15 th , 2013 and concluding on or before January 15, 2016.
Subject Duration:	The duration of each subject's participation will be 6 weeks, based on a 1 week inpatient stay for treatment/observation, plus 5 weeks of twice-weekly follow-up.

Primary Objective and Primary Endpoints:

1] The primary objective is to determine and compare the cure rates for AQ-13 and Coartem. Cure is a lack of recrudescence within 42 days (PCR-corrected) – no evidence of recrudescence with the same parasite genotype(s) after reduction of the asexual parasitemia to less than 25% of the admission value by day 3 and clearance of asexual parasites and fever by day 7. Failure is defined as lack of cure.

Secondary Objectives and associated Endpoints for comparisons of AQ-13 with Coartem:

[figure not shown]
- 1] Adverse Events (AEs) – within 4 weeks of treatment as judged by **blinded** physician reviewers to be possibly related to the study drug(s).
- 2] Parasite clearance time – time from the initiation of treatment to the first of 2 successive negative thick smears.
- 3] Time to recrudescence or reinfection – time from the initiation of treatment to the reappearance of asexual *P. falciparum* parasites on the thick smear.
- 4] Effects on the QT (QTc) interval – mean changes from the baseline (pre-treatment) QTc interval to the post-treatment QTc interval after treatment with AQ-13 or Coartem.
- 5] Pharmacokinetic parameters for AQ-13 – will include measurements of AQ-13 blood levels over time (peak levels, AUC, MRT), drug distribution (Vd/F) and drug elimination (t $\frac{1}{2}$, Cl/F).
- 6] Fever clearance time: time in hours from the initiation of therapy until the disappearance of fever for at least 24 hours.

Tertiary Objectives and associated Endpoints for comparisons of AQ-13 with Coartem:

- 1] Pharmacokinetics of AQ-13 metabolites – estimates of pharmacokinetic parameters for the mono- and di-*N*-dealkylated metabolites of AQ-13 (AQ-72, AQ-73).
- 2] Aminoquinoline (CQ) pruritus – pruritus in persons receiving AQ-13 or Coartem, especially in persons with a history of pruritus after treatment with CQ.

Schematic of Study Design (Flow Chart 1, below):

This is a **randomized study in which subjects** who have provided their informed consent to participate **will be randomized to one of two study arms**: 1] oral administration of AQ-13 (1596 mg AQ-13 base over 3 days) or 2] the control arm, in which subjects will receive the standard treatment dose of Coartem (artemether + lumefantrine; 4 tablets twice daily x 3 days) which is currently recommended as the first-line treatment for uncomplicated *P. falciparum* malaria in Mali, including infections likely to be resistant to chloroquine (CQ) or pyrimethamine + sulfadoxine (Fansidar[®]). This is a single-blind study because the subjects (**but not the investigators**) will know which subjects are receiving AQ-13 vs. Coartem (by the number and types of capsules [AQ-13] or tablets [Coartem]).

Flow Chart 1**PROOF OF CONCEPT EFFICACY STUDY FOR AQ-13**

2 BACKGROUND, RATIONALE, RISKS/BENEFITS

2.1 Background

Antimalarial resistance was the single most important factor in the recent global resurgence of malaria [1] and is now the greatest obstacle to the control and potential elimination of malaria [2]. Specifically, the increasing prevalence of chloroquine (CQ) resistance [3] and the recent appearance of artemisinin resistance [4-5] have had a profoundly negative impact on malaria morbidity and mortality [6-7]. Therefore, the development of new antimalarials active against otherwise drug-resistant parasites that are also safe and orally bioavailable is an urgent global health priority. In particular, it would be desirable to have alternative antimalarials that were as safe and orally bioavailable as CQ, and were also active against CQ-, mefloquine- and multi-resistant strains of *Plasmodium falciparum*.

Our recent studies have shown that aminoquinolines (AQs) with side chains shorter or longer (≤ 3 or ≥ 10 carbons) than the 5 carbon isopentyl side chain of chloroquine (CQ) are active *in vitro* against CQ-, mefloquine- and multi-resistant *P. falciparum* [8-10]. They have also shown that short chain AQs administered orally are effective *in vivo* in two monkey models of human malaria (the *P. cynomologi*/rhesus monkey model of human *P. vivax* infection, and the *P. falciparum*/squirrel monkey model of human infection with the CQ-resistant Indochina I strain after adaptation to the squirrel monkey).

In addition, recent Phase 1 (safety and pharmacokinetic) studies have shown that the side effects (adverse events [AEs] associated with) of the lead compound AQ-13 (which has a linear *n*-propyl side chain) in human subjects are similar to those of CQ and that the pharmacokinetics of AQ-13 and CQ are similar [11]. In terms of potential cost, the current estimate of the cost of goods for AQ-13 is \$0.03 per dose (for an AQ-13 oral dose equivalent to 700 mg CQ base in terms of bioavailability), which is approximately \$0.08 per treatment course if the treatment dose chosen is 1596 mg over 3 days. In addition, the close structural similarity between AQ-13 and CQ and the similar Adverse Events (AEs) observed with AQ-13 and CQ in the Phase 1 studies [11] suggest that AQ-13 may be as safe as CQ for the treatment of human subjects with malaria, and raise the possibility that AQ-13 may share the safety of CQ during pregnancy. Although these arguments are part of the rationale for studying AQ-13, please note that **adult women (including women who are pregnant or breast-feeding) are excluded from participation in these studies**. Finally, please note that AQ-13 is only one of 66 AQs which we have synthesized and shown to be active against CQ- and multi-resistant *P. falciparum* [9-10]. Therefore, if these studies are successful, they have the potential to create a new class of AQ antimalarials effective against otherwise drug-resistant *P. falciparum* malaria parasites.

2.2 Rationale

Therefore, the next logical step in the evaluation of AQ-13 is to determine whether it is active against CQ-resistant *P. falciparum* infection in human subjects. The hypotheses underlying this protocol are that: 1] an AQ-13 dose of 1596 mg administered orally will be efficacious for the treatment of uncomplicated *P. falciparum* malaria in human subjects, and 2] the bioavailability, pharmacokinetics and adverse events (AEs) of AQ-13 in human subjects with uncomplicated malaria will be similar to those observed previously in healthy uninfected subjects during the Phase 1 studies [11].

The rationales for the selection of adult men for this Proof of Efficacy Study with AQ-13 are that: 1] the involvement of only males will obviate potential concerns about inadvertent pregnancies in female volunteers who have agreed to contraception and 2] that persons who have survived to adulthood in Mali are protected against life-threatening complications and death from malaria because they have acquired the semi-immune state [12]. Therefore, if for reasons we have not foreseen, AQ-13 does not work (if AQ-13 is not effective for treatment of uncomplicated malaria in human subjects), the risk of severe disease or death in these subjects will still be extremely low – because they are protected by their previous acquisition of the semi-immune state.

2.3 Potential Risks and Benefits

2.3.1 Potential Risks

Immediate (Short-Term) Risks. The first potential risk of participation in this study is that the investigational drug AQ-13 may not work; it may not cure uncomplicated *P. falciparum* malaria in Malian adults. If AQ-13 does not clear malaria parasites from subjects' blood by day 7 in the AQ-13 arm, those subjects will be treated with Quinine. In addition, if Coartem does not clear malaria parasites from subjects' blood in the Coartem control arm by day 7, these subjects will also be treated with Quinine, which is recommended in Mali for rescue in persons who fail treatment for uncomplicated malaria.

The most frequent side effects of AQ-13 in the volunteers who received it during the Phase 1 studies (and therefore the most likely adverse events (AEs) in these Proof of Concept studies) are similar to those of CQ: they include headache, dizziness, and digestive tract symptoms (nausea, loss of appetite, diarrhea, vomiting and abdominal pain). One of 126 subjects developed a mild, transient rash on her lower body, and 1 had muscle damage for several days, which is thought not to have been caused by the study drug, and is often caused by vigorous exercise. Other potential risks include bleeding, bruising, discomfort, black and blue spots and infection from venipunctures to obtain blood specimens. Abnormal beating of the heart is a potential risk, and has been observed in two subjects during the previous studies. Although it is thought not to have been caused by the study drug, the study drug will be stopped and subjects will be treated with quinine if they have abnormal beating of the heart and were randomized to AQ-13.

Potential Long-Term Risks. There are no long-term risks which are likely, in part because the subjects participating in this study will receive AQ-13 for only 3 days in daily doses that are 6 to 10-fold lower than the doses of CQ used previously to treat rheumatoid arthritis and other non-infectious diseases [13-14]. However, there have been reports of ocular complications when other 4-AQs (CQ or hydroxy-CQ; retinopathy) or an 8-AQ (tafenoquine keratopathy) [15] have been given for periods as short as 3 months (tafenoquine) or as long as 4-10 years (CQ or hydroxy-CQ doses of >3 or >6.5 mg base/kg/day) [16]. Therefore, although the likelihood of such complications is extremely low, we will perform eye examinations before and after treatment with AQ-13 to ensure that there is no evidence for ocular AEs with AQ-13. Note that the eye examinations performed before and after AQ-13 dosing during the Phase 1 studies revealed no evidence of ocular AEs.

Potential for Unknown Risks. Because AQ-13 is an investigational drug, there may be other risks that we do not know about. Those risks have been substantially reduced – although not eliminated – by the absence of such AEs during the Phase 1 studies in healthy human volunteers.

Potential Loss of Confidentiality. Although there is a risk that information about subjects' participation in this study could become known, that risk is low. That risk will be minimized by keeping study information in password-protected computers and locked cabinets. When the results of the study are published or made available on the Internet, participants will be identified by study ID (identification) number and not by name. Officials of the US and Mali Governments, Tulane University and the University of Bamako will have access to the study records. Referrals to Malian physicians will be provided for problems related to this study and subjects will receive new information about AQ-13 that may affect their willingness to participate as that information becomes available.

Rationale (Justification) for Risks. Although these risks (including the similar AEs observed with AQ-13 and CQ) [10] are real, they are small in relation to the risks of untreated malaria for individual patients [1-2]. For the community, drug-resistant parasites are the most important obstacle to the control and potential elimination of malaria. In addition, after a candidate antimalarial has been found active *in vitro* and *in vivo* in monkey models of human malaria [8-9] and safe in healthy human subjects [11], the only way to determine whether that candidate compound has the potential to be used as an antimalarial to treat humans with CQ-resistant malaria is to perform a Phase 2 Proof of Concept Study and ultimately Phase 3 studies. Thus, at this point in the evaluation of AQ-13 as the lead compound, it is appropriate to perform a Proof of Concept Efficacy Study of AQ-13 in human subjects.

2.3.2 Known Potential Benefits.

The potential benefit to the subjects from participating in this study is the information obtained from the initial blood testing and heart and eye examinations. If there are abnormal results on those tests, they will be explained to the subjects in detail, and the subjects will be referred for initial evaluation and treatment by medical specialists in Mali. Alternatively, for subjects whose only abnormal test result is a positive malaria smear, treatment with either AQ-13 or Coartem may benefit them by clearing those malaria parasites from their blood. In addition, knowledge gained from this study may benefit both these subjects and others in the future. However, there are no expected benefits to the subjects (participants) from measuring the levels of AQ-13 and its metabolites in their blood or urine or from studying the genes that metabolize these drugs or control the host immune response to malaria infection.

3 OBJECTIVES (ENDPOINTS):

Statement of Purpose. To summarize the information in the Background and Significance section above, the next logical step in the evaluation of AQ-13 as the lead compound is to determine whether it is active against (efficacious for the treatment of) uncomplicated *P. falciparum* malaria in human subjects. That is the purpose of (rationale for) this Proof of Concept Study. The hypotheses underlying this protocol are that: 1] an AQ-13 dose of 1596 mg administered orally will be efficacious for the treatment of uncomplicated *P. falciparum* malaria in human subjects, and 2] the bioavailability, pharmacokinetics and adverse events (AEs) of AQ-13 in human subjects with uncomplicated malaria will be similar to those observed previously in healthy uninfected subjects (during the Phase 1 studies) [11]. The rationale for beginning with studies of adults before proceeding to studies of children is based on safety. Our rationale is that it is safer to begin with studies of adults (who have acquired the semi-immune state) before performing studies of children (who may not yet acquired the semi-immune state and are therefore at greater risk of severe or complicated malaria if AQ-13 is not efficacious for the treatment of uncomplicated malaria). The rationale for performing the Proof of Efficacy Study with only males is to ensure there is no chance that an adult female volunteer who has agreed to practice contraception before and after exposure to AQ-13 will inadvertently become pregnant during or shortly after these studies.

Primary Objective and associated Endpoints:

1] The primary objective is to determine and compare the cure rates for AQ-13 and Coartem. Cure is a lack of recrudescence within 42 days (PCR-corrected - no evidence of recrudescence with the same parasite genotype(s)) after reduction of the asexual parasitemia to < 25% of the admission value by day 3 and clearance of asexual parasites and fever by day 7. Failure is defined as "lack of cure."

Secondary Objectives and associated Endpoints for comparisons of AQ-13 with Coartem:

- 1] Adverse Events (AEs) – within 4 weeks of treatment as judged by **blinded** physician reviewers to be possibly related to the study drug(s) using the same criteria as in the Phase 1 study.
- 2] Parasite clearance time – from the initiation of treatment to the first of 2 successive negative thick smears.
- 3] Time to recrudescence or reinfection – time from the initiation of treatment to the reappearance of asexual *P. falciparum* parasites on the thick smear.
- 4] Effects on the QT (QTc) interval – mean changes from the baseline (pre-treatment) QT interval to the post-treatment QT interval after treatment with AQ-13 or Coartem.
- 5] Pharmacokinetic parameters for AQ-13 – these will include measurements of blood levels over time (peak levels, AUC, MRT), drug distribution (Vd/F) and drug elimination (t_{1/2}, Cl/F).
- 6] Fever clearance time: Time in hours from the initiation of therapy until disappearance of fever for at least 24 hours.

Tertiary Objectives and associated Endpoints for comparisons of AQ-13 with Coartem:

- 1] Pharmacokinetics of AQ-13 metabolites – estimates of pharmacokinetic parameters for the mono- and di-*N*-dealkylated metabolites of AQ-13 (AQ-72, AQ-73).
- 2] Aminoquinoline (CQ) pruritus – pruritus in persons receiving AQ-13 or Coartem, especially in persons who have a history of pruritus after treatment with CQ.

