6.5 Inpatient Period

Blood samples will be taken for drug and metabolite levels on days 1-5 and hematology and chemistry panels on day 4. After screening Holter recordings have been obtained and reviewed for pre-existing arrhythmias, continuous 24 hour Holter recordings will be performed on each of days 1-4 (focusing on the time between 2 and 6 hours after dosing for maximal effects on the QT interval). Urine collections will be performed on each of days 1-4. An eye exam plus an additional 1 hour Holter recording will be performed at the end of week 1.

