6.8 Discontinuation or Withdrawal of a Subject

Treatment with AQ-13 or Coartem in this study may be discontinued for any of the reasons below. However, whenever possible (i.e., except when informed consent to participate has been withdrawn) subjects will be followed through to the conclusion of the treatment of their illness and outcomes will be examined using both *intent to treat* and *per protocol* analyses.

- 1] Recurrence of uncomplicated malaria,
- 2] Progression to severe or complicated malaria,
- 3] Development of ventricular tachyarrhythmias or conduction defects (new 2nd or 3rd degree heart block),
- 4] Other Serious Adverse Events (SAEs) possibly related to AQ-13, or
- 5] The subject's decision to withdraw his/her informed consent to participate.

If lack of cure (recurrence of uncomplicated malaria) occurs with either AQ-13 or Coartem, the subject will be treated with Quinine. Likewise, if a subject develops severe or complicated malaria, he will be treated with Quinine as recommended by the Mali Ministry of Health and the National Malaria Control Programme. Treatment with either AQ-13 or Coartem will be stopped in subjects who develop ventricular tachyarrhythmias, conduction defects or other serious adverse events (SAEs) possibly related to AQ-13 or Coartem. In those instances, further antimalarial treatment (if necessary) will be provided using Quinine based on the recommendations of the Mali Ministry of Health and the Mali National Malaria Control Programme.

Flow Chart 4.Work Sheet (schedule of procedures) for Phase 2 efficacy studies of AQ-13 in semi-immune Malian adult Males ≥ 18 years of age

Clinical	Scr	Pre-dose	0	30 m	1 hr	2	4	6	12	18	24	24:30	25	26	28	30	36	48	48:30	49	50	52	54	60	72	96	1/2 wks	
History/PE	X																										X	
Medication History	X																										X	
Assess for AEs		X							X										X						X		X ₁	
Laboratory																												
CBC,WBC, diff, plt	X																										X	
Chem 7	X																										X	
Liver profile	X																										X	
G6PD	X																											
AQ & Metabolites			X	X	X	X	X	X	X	X	X	X	X	X	X	X	X	X	X	X	X	X	X	X	X	X		
Freeze parasites			X																									
24 hr urine		X									X									X						X		
Diagnostics																												
Holter Recording	X		X ₂								X ₂								X ₂						X ₂		X ^{**}	
Eye exam	X																											X
Study Drug AQ-13 $\Sigma=1750$ mg			X ₃								X ₃								X ₃									

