7.2.2 Clinical Data

Clinical assessments of study participants at the times of screening, inpatient studies and outpatient follow-up will be performed by Malian physicians (likewise blinded to the treatments the participants have received) using the Case Report Forms prepared for this study.

Assessment of Clinical Outcomes

Judgments about progression to severe or complicated malaria and the recurrence of uncomplicated malaria will be made by the Mali PI and a physician colleague (both blinded to the treatment the patient received) based on the CRFs and parasitologic data. As for the parasitologic data, those results will then be summarized by the subject's study numbers and returned to the study statistician who will place the data in groups by study arm (retaining blindedness by using Arm 1 and Arm 2 to identify the study arm rather than AQ-13 and Coartem) before the data are tested for differences and presented to the DSMB.

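### Sections 2.3.1 and 6.8 give different cardiac stopping and quinine rules; one is tied to the AQ-13 arm, and nothing says which governs.

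*Combined protocol and SAP*

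**What the plan says.** Section 2.3.1 (Potential Risks) reports that abnormal heart rhythm was seen in two subjects in previous studies. It then gives an instruction: study drug stops, and "subjects will be treated with quinine if they have abnormal beating of the heart and were randomized to AQ-13". The finding is not defined and Coartem is not mentioned.

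Section 6.8 (Discontinuation or Withdrawal of a Subject) covers the same ground twice.

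- The list opens with "Treatment with AQ-13 or Coartem in this study may be discontinued for any of the reasons below". Its cardiac item is "Development of ventricular tachyarrhythmias or conduction defects (new 2nd or 3rd degree heart block", and its next item is "Other Serious Adverse Events (SAEs) possibly related to AQ-13".
- The paragraph below the list says "Treatment with either AQ-13 or Coartem will be stopped in subjects who develop ventricular tachyarrhythmias, conduction defects", and adds other serious adverse events possibly related to either drug. Quinine follows only where further antimalarial treatment is needed.

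On blinding, Section 7.2.2 has clinical assessments, including those in the inpatient period, "performed by Malian physicians (likewise blinded to the treatments the participants have received". Section 4 says the investigators who evaluate adverse events and other data do not know the arm. Section 10.4 gives only the pharmacist access to the randomization form.

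**The concern.** A stopping rule that depends on the arm produces stopping and rescue that depend on the arm. In an open question of non-inferiority with 33 men per arm, that can affect cure, QTc and adverse-event comparisons for reasons unrelated to how the drugs perform.

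It also works against the blinding. A physician who must know that a man is on AQ-13 before acting has to be told. A colleague who sees one man stopped for a rhythm finding and another continued can guess the allocation.

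Finally, two physicians at the inpatient unit could each follow the protocol and manage the same finding differently.

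**Working it through.** The plan states no figure on this point, so the main check sets the texts side by side.

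| Feature | Section 2.3.1 | Section 6.8 |
|---|---|---|
| Arms | AQ-13 named; Coartem not mentioned | Both in the opening line and the paragraph; the serious-event item in the list names AQ-13 only |
| Trigger | Any abnormal heartbeat, undefined | Ventricular tachyarrhythmia, conduction defect (listed as new second- or third-degree block), or other possibly related serious adverse event |
| Force | Mandatory | Permissive in the list, mandatory in the paragraph |
| Quinine | Automatic | Only where further antimalarial treatment is needed |

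Five cases show where the texts conflict.

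1. AQ-13, new non-serious atrial arrhythmia or frequent premature beats. Section 2.3.1 stops drug and gives quinine. Section 6.8 gives no reason to stop. This is a direct conflict. Such findings are within the protocol's own scope, because exclusion criterion 7 in Section 5.2 names both at screening.
2. Coartem, same finding. Section 2.3.1 is silent and Section 6.8 gives no reason to stop. Compared with case 1, the same finding leads to different management by arm if both sections are followed.
3. AQ-13, new second-degree block. Section 2.3.1 and the Section 6.8 paragraph both stop drug. They differ on whether quinine is automatic.
4. Coartem, new heart block. The Section 6.8 paragraph stops drug and Section 2.3.1 is silent. This is a gap, not a contradiction.
5. Coartem, another serious adverse event possibly related to Coartem. The paragraph in Section 6.8 stops drug. The list item does not cover it.

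Following both sections, the AQ-13 trigger is the Section 6.8 list plus any other abnormal heartbeat, and the Coartem trigger is the Section 6.8 list alone.

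No other text resolves this. The halting rules in Section 8.6 govern enrollment, not an individual man's dosing. No section says that 6.8 prevails over 2.3.1.

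**What one affected man could do to a cure rate.** The cure definition in Section 7.1.1 does not say how a man stopped early and given quinine is counted. Take 33 in his arm, an assumed 32 cured if he is a cure, and 31 if he is not:

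- Would have been cured on study drug, counted as a failure: 31/33 − 32/33 = 93.9% − 97.0% = −3.0 points.
- Would have been cured, excluded instead: 31/32 − 32/33 = 96.9% − 97.0% = −0.1 points.
- Would have failed, but cleared by quinine and counted as a cure: 32/33 − 31/33 = +3.0 points.
- Would have failed, excluded instead: 31/32 − 31/33 = 96.9% − 93.9% = +2.9 points.

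So the direction as well as the size depends on a rule the plan does not give.

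**Scale against the 15% margin, only if he counts as a failure.** The upper Wald limit for Coartem minus AQ-13 is (pC − pE) + 1.96 × √[pC(1 − pC)/n + pE(1 − pE)/n].

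- 28 evaluable per arm (Section 5.1), an assumed 27 cured in each: 0 + 1.96 × √(2 × 0.00123) = 9.7%. The Newcombe limit is 14.4%.
- One further AQ-13 failure: 0.0357 + 1.96 × √(0.00123 + 0.00237) = 15.3%. Newcombe gives 19.3%.
- 33 per arm, 32 Coartem and 31 AQ-13 cures: 0.0303 + 1.96 × √(0.00089 + 0.00173) = 13.1%. Newcombe gives 16.8%.

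Section 10.3 names no interval method, so both are shown.

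**The case against.** The best defense is that Section 2.3.1 is a risk narrative in lay wording, in a paragraph largely about AQ-13 side effects, while Section 6.8 is the operational section and covers both arms. On that reading 6.8 governs, there is no arm-specific cardiac rule, and the serious-event item in its list is a drafting slip. This is a plausible account of intent, but the protocol does not say it. Section 2.3.1 is worded as a directive. Its preceding paragraph names both arms explicitly when it deals with failure to clear parasites by day 7, so naming only AQ-13 for the heart can be read as deliberate.

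Several stronger readings are tempting, and the documents do not support them.

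- That a man on Coartem must continue under Section 2.3.1. The section does not say so; it is silent on that arm.
- That sites would act differently. The synopsis gives one inpatient site, where dosing and the 24-hour recordings take place. The second site handles outpatient follow-up.
- That minor rhythm findings will be frequent because "continuous 24 hour Holter recordings will be performed on each of days 1-4". No rate is given. The only count is the two subjects in previous studies, and men with more than 20 extrasystoles per hour are excluded at screening.
- That Holter results will reach the physician too late to act. Section 6.2.2 assigns Holter recordings to an SOP that is not in the documents, so reading times cannot be called missing. A reading deadline would also be a new clinical rule rather than a reconciliation.
- That every stop costs 3.0 points of cure. That needs the counting assumption made above.

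**Conclusion.** The inconsistency is real. The two sections differ on arms covered, trigger and quinine, and nothing in the protocol ranks them. The firm contradiction is narrow: men on AQ-13 with a non-serious rhythm finding outside the Section 6.8 list, plus the quinine wording for those inside it. The disagreements within Section 6.8 are smaller but belong in the same correction.

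Two consequences follow from the text. AQ-13 has a wider trigger than Coartem if both sections are followed, and the arm condition cannot be applied under the blinding described in Sections 4, 7.2.2 and 10.4 without revealing the arm. The second assumes that the physicians assessing the men also take or prompt the stopping decision; neither section names who takes it.

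The effect on the cure comparison cannot be sized. The documents give no usable rate of such findings and no rule for counting a man who is stopped and given quinine. If he counted as a failure, each would be 1/33 = 3.0 points of his arm. If Section 6.8 is meant to govern alone, the arm-dependence disappears and only the wording needs repair.

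**What to change.** Reconcile Section 2.3.1 with Section 6.8, and the list with the paragraph inside Section 6.8, into one rule placed in Section 6.8. Replace the instruction in Section 2.3.1 with a reference to it. The rule should state one trigger list, the arms it covers, whether stopping is permitted or required, and when quinine follows. It should be worded so that it can be applied under the stated blinding. If the sponsor keeps any arm-specific element, the protocol needs to say who applies it and how allocation stays concealed from the assessing physicians.

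The trigger, the arms covered and the rescue treatment are for the sponsor and the DSMB to decide; this review takes no position on them.

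The cost is a wording amendment to two sections, with the usual ethics approval. The consent text is not available here and should be checked for the same discrepancy. Sample size, visits and procedures are unchanged.
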